1.2 Schema

The study design is depicted in Figure 1.

IL=first line of therapy; BICR=blinded independent central review; dMMR=mismatch repair deficient; ECOG PS=Eastern Cooperative Oncology Group Performance Status; mCRC=metastatic colorectal cancer; MSI-H=microsatellite instability-high; PD-1=programmed cell death 1 protein; Q3W= every 3 weeks; Q6W=every 6 weeks; Q9W=every 9 weeks; R=randomization; RECIST=Response Evaluation Criteria In Solid Tumors.

^a Coformulated quavonlimab/pembrolizumab (quavonlimab 25 mg with pembrolizumab 400 mg).

^b Per RECIST 1.1 by BICR.

^c Coformulated favezelimab/pembrolizumab (favezelimab 800 mg with pembrolizumab 200 mg).

^d Coformulated vibostolimab/pembrolizumab (vibostolimab 200 mg with pembrolizumab 200 mg).

^e Combination MK-4830+pembrolizumab (MK-4830 800 mg + pembrolizumab 200 mg).

Note: Refer to Section 6.1.1 for study intervention information and Section 8.11.4 for posttreatment follow-up information for participants in closed arms.

1.3 Schedule of Activities

At implementation of Amendment 05, the following treatment arms are considered closed: Cohort B: MK-4280A, Cohort B: MK-7684A, and Cohort B: MK-4830+pembrolizumab.

As of the Investigator Letter dated 16-DEC-2024, participants who were receiving MK-4280A were offered the option to continue study therapy until treatment completion or transition to pembrolizumab monotherapy, and participants who were receiving MK-7684A were discontinued from that study therapy and offered the option to transition to pembrolizumab monotherapy.

As per the Investigator Letter dated 25-SEP-2023, the MK-4830+pembrolizumab arm was closed to enrollment; all ongoing participants were offered the option to continue study therapy until treatment completion or transition to pembrolizumab monotherapy.

Refer to Section 8.2.1 for imaging information and Section 8.3 for safety monitoring information for participants in closed arms.

The following procedures/assessments are not required for participants in closed arms:

- PRO assessments
- PK/ADA sample collection
- Biomarker sample collection
- Follow-up for progression, subsequent antineoplastic therapy status, and survival

Refer to Section 6.1.1.2 for Second Course treatment information for participants in closed arms.

1.3.1 Cohort A

Table 1 Study Schedule of Activities – Cohort A

Study Period:	Screening	Intervention (Q6W)					EOT	Posttreatment			Notes
Visit Number/Title:	Screening	Cycle 1		Cycle 2		Cycles 3 to 17		Safety FU	Efficacy FU	Survival FU	
Cycle Day	Up to 28 days prior to first dose	1	22	1	22	1	DC	30 days after last dose			
Scheduling Window (days):	-28 to -1	+3	±3	±3	±3	±3		+7	Q9W ±7	Q12W ±14	
Administrative Procedures											
Informed Consent	X										If the investigator plans to treat beyond disease progression, the participant or their legally acceptable representative will be asked to provide documented informed consent (see Section 8.1.1.1).
Informed Consent for Future Biomedical Research (optional)	X										To be obtained after consenting to the main study.
Inclusion/Exclusion Criteria	X	X									
Participant Identification Card	X	X									Add the allocation number at the time of allocation.
Demographics and Medical History	X										
Oncologic Medical History (oncology disease status, MSI/MMR status, and prior oncology treatment history including surgery)	X										

Study Period:	Screening	Intervention (Q6W)					EOT	Posttreatment			Notes
Visit Number/Title:	Screening	Cycle 1		Cycle 2		Cycles 3 to 17		Safety FU	Efficacy FU	Survival FU	
Cycle Day	Up to 28 days prior to first dose	1	22	1	22	1	DC	30 days after last dose			
Scheduling Window (days):	-28 to -1	+3	±3	±3	±3	±3		+7	Q9W ±7	Q12W ±14	
CCI											
Prior/Concomitant Medication Review	X	X	X	X	X*	X	X	X			Record concomitant medications beyond 30 days after treatment discontinuation if related to an SAE or ECI. *May be conducted by telephone or video at the discretion of the investigator or qualified designee.
Randomization (via IRT)		X									To be completed after confirmation of eligibility.
Study Medication Administration		X		X		X					
Progression and Subsequent Antineoplastic Therapy Status							X	X	X	X	All progression events and anticancer therapy will be recorded during follow-up until time of death or termination of survival follow-up. If a clinical visit is not feasible, follow-up information may be obtained by other means such as telephone or email.

MK-1308A-008-05 FINAL PROTOCOL
08VH4V

[figure not shown]
Study Period:	Screening	Intervention (Q6W)					EOT	Posttreatment			Notes
Visit Number/Title:	Screening	Cycle 1		Cycle 2		Cycles 3 to 17		Safety FU	Efficacy FU	Survival FU	
Cycle Day	Up to 28 days prior to first dose	1	22	1	22	1	DC	30 days after last dose			
Scheduling Window (days):	-28 to -1	+3	±3	±3	±3	±3		+7	Q9W ±7	Q12W ±14	
Safety Assessments											
Full Physical Examination	X						X				
Height	X										
Weight	X	X		X		X	X	X			
Directed Physical Examination		X	X	X		X		X	X*		*May be conducted by telephone or video at the discretion of the investigator or qualified designee.
Vital Signs (temperature, HR, RR, DBP, SBP)	X	X	X	X		X	X	X			BP and pulse rate will be measured after the participant has been resting for 5 minutes. Include pulse oximetry (SpO2) if locally required.
12-lead ECG	X					X*	X				*Repeat if clinically indicated.
ECOG Performance Status	X	X		X		X	X	X			Must be performed within 3 days of C1D1 treatment and before treatment at each cycle.
AE/SAE review	X										AEs monitored up to 30 days after last dose. SAEs monitored up to 90 days and pregnancy monitored up to 120 days after last dose, or 30 days after last dose if participant starts a new anticancer therapy, whichever is sooner. On C2D22, may be conducted by telephone or video at the discretion of the investigator or qualified designee.

Study Period:	Screening	Intervention (Q6W)					EOT	Posttreatment			Notes
Visit Number/Title:	Screening	Cycle 1		Cycle 2		Cycles 3 to 17		Safety FU	Efficacy FU	Survival FU	
Cycle Day	Up to 28 days prior to first dose	1	22	1	22	1	DC	30 days after last dose			
Scheduling Window (days):	-28 to -1	+3	±3	±3	±3	±3		+7	Q9W ±7	Q12W ±14	
Laboratory Assessments											
Hematology/Chemistry	X	X*		X		X	X	X			Collect predose. * Collect within 72 hours before first study intervention dose.
Urinalysis	X	X*		X*		X*	X	X			Collect within 72 hours before first study intervention dose. *As clinically indicated.
Serum or Urine Pregnancy test (WOCBP only)	X	X		X	X	X	X	X			WOCBP require a negative test prior to randomization. If more than 24 hours for a urine test or 72 hours for a serum test have elapsed prior to the first dose of study intervention, another pregnancy test is required. See additional country-specific requirements in Appendix 7.
PT/INR and aPTT/PTT (baseline only)	X										Additional testing to be conducted as clinically indicated.
HIV, HBsAg, HCV	X*										*Only if required by local health authority. See country-specific requirements in Appendix 7.

Study Period:	Screening	Intervention (Q6W)					EOT	Posttreatment			Notes
Visit Number/Title:	Screening	Cycle 1		Cycle 2		Cycles 3 to 17		Safety FU	Efficacy FU	Survival FU	
Cycle Day	Up to 28 days prior to first dose	1	22	1	22	1	DC	30 days after last dose			
Scheduling Window (days):	-28 to -1	+3	±3	±3	±3	±3		+7	Q9W ±7	Q12W ±14	
Thyroid Function Tests (TSH, T3, T4), Cortisol, and ACTH**	X	X*	X	X		X	X	X			Free T3 and Free T4 are acceptable if total T3 and total T4 are unavailable. After Cycle 1, retrospective review of thyroid function, ACTH and cortisol testing results is allowed when the results are not available before dosing. *Collection is optional on C1D1. **ACTH testing is to be done as required per investigator's discretion
Serum Tumor Marker (CEA)	X	X		X		X	X		X		Dosing permitted prior to results of CEA being known.

PK/ADA/Biomarkers

CCI

Study Period:	Screening	Intervention (Q6W)					EOT	Posttreatment			Notes
Visit Number/Title:	Screening	Cycle 1		Cycle 2		Cycles 3 to 17		Safety FU	Efficacy FU	Survival FU	
Cycle Day	Up to 28 days prior to first dose	1	22	1	22	1	DC	30 days after last dose			
Scheduling Window (days):	-28 to -1	+3	±3	±3	±3	±3		+7	Q9W ±7	Q12W ±14	

CCI

ACTH=adrenocorticotrophic hormone; ADA=antidrug antibodies; AE=adverse event; aPTT=activated partial thromboplastin time; BP=blood pressure; BRAF=B-Raf gene; C=cycle; CEA=carcinoembryonic antigen; CT=computed tomography; (ct)DNA=(circulating tumor) deoxyribonucleic acid; D=day; DBP=diastolic blood pressure; DC=discontinuation; ECG=electrocardiogram; ECI=event of clinical interest; ECOG=Eastern Cooperative Oncology Group; EORTC QLQ-C30=European Organisation for Research and Treatment of Cancer Quality of Life Questionnaire; EOT=end of treatment; (e)PRO=electronic patient-reported outcome; EQ-5D-5L=EuroQoL 5-dimension, 5-level scale; FU=follow-up; HBsAg=Hepatitis B surface antigen; HCV=Hepatitis C virus; HIV=human immunodeficiency virus; HR=heart rate; INR=international normalized ratio; IRT=interactive response technology; KRAS=Kirsten rat sarcoma viral oncogene homolog; MMR=mismatch repair; MRI=magnetic resonance imaging; MSI=microsatellite instability; NAb=neutralizing antibody; PRO=patient-reported outcome; PT=prothrombin time; PTT=partial thromboplastin time; Q6W=every 6 weeks; Q9W=every 9 weeks; Q12W=every 12 weeks; RAS=genes that makes the proteins called KRAS, HRAS, and NRAS; RNA=ribonucleic acid; RR=respiratory rate; SAE=serious adverse event; SBP=systolic blood pressure; SoA=schedule of activities; SpO2=oxygen saturation; T3=triiodothyronine; T4=thyroxine; TSH=thyroid-stimulating hormone; WOCBP=women of childbearing potential.

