Vital Signs (temperature, HR, RR, DBP, SBP)	X	X	X	X	X	X	X			BP and pulse rate will be measured after the participant has been resting for 5 minutes. Include pulse oximetry (SpO2) if locally required.
12-lead ECG	X		X*	X*	X*	X				*As clinically indicated.
ECOG Performance Status	X	X	X	X	X	X	X			Must be performed within 3 days of C1D1 treatment and before treatment at each cycle.
AE/SAE review	X									AEs monitored up to 30 days after last dose. SAEs monitored up to 90 days and pregnancy monitored up to 120 days after last dose, or 30 days after last dose if participant starts a new anticancer therapy, whichever is sooner. Refer to Section 8.3 for safety monitoring information for participants in closed arms.
Laboratory Assessments										
Hematology/Chemistry	X	X*	X	X	X	X	X			Collect Predose. *Collect within 72 hours before first study intervention dose.
Urinalysis	X	X*	X*	X*	X*	X*	X			*As clinically indicated Collect within 72 hours before first study intervention dose.
Serum or Urine Pregnancy test (WOCBP only)	X	X		X		X	X			WOCBP require a negative test prior to allocation. If more than 24 hours for a urine test or 72 hours for a serum test have elapsed prior to the first dose of study intervention, another pregnancy test is required. See country-specific requirements in Appendix 7.

Study Period:	Screening	Intervention				EOT	Posttreatment			Notes
Visit Number/Title:	Screening	Cycle 1		Cycle 2 onwards*			Safety FU	Efficacy FU	Survival FU	*Cycles 2 to 17 for Q6W schedule; Cycle 2 to 35 for Q3W schedule.
Cycle Day	Up to 28 days prior to first dose	1	Day 22 (Q6W regimens only)	1	Day 22 (Q6W regimens only)	DC	30 days after last dose			
Scheduling Window (days):	-28 to -1	+3	±3	±3	±3		+7	Q9W ±7	Q12W ±14	
PT/INR and aPTT/PTT (baseline only)	X									Additional testing to be conducted as clinically indicated.
HIV, HBsAg, HCV	X*									*Only if required by local health authority. See country-specific requirements in Appendix 7.
Thyroid Function Tests (TSH, T3, T4), Cortisol, and ACTH**	X		X	X		X	X			Free T3 and Free T4 are acceptable if total T3 and total T4 are unavailable. After C1, retrospective review of thyroid function, ACTH and cortisol testing results is allowed when the results are not available prior to dosing. **ACTH testing is to be done as required per investigator's discretion.
Serum Tumor Marker (CEA)	X	X	X	X		X		X		Dosing permitted prior to results of CEA being known.

Study Period:	Screening	Intervention				EOT	Posttreatment			Notes

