1.3.3 Second Course Treatment

Table 3 Study Schedule of Activities – Second Course Treatment

[figure not shown]
Study Period:	Intervention		EOT	Posttreatment			Notes
Visit Number/Title:	Cycle 1	Cycles 2 to 17 (2 to 9 for Q6W schedule)		Safety FU	Efficacy FU	Survival FU	
Cycle Day	1	1	DC	30 days after last dose			
Scheduling Window (days):	±3	±3		+7	Q9W ±7	Q12W ±14	
Administrative Procedures							
Eligibility Criteria	X						
Concomitant Medication Review	X	X	X	X			Record concomitant medications beyond 30 days after treatment discontinuation if related to an SAE or ECI.
Study Intervention Administration	X	X*					*Required every 6 weeks for participants randomized to the MK-1308A or pembrolizumab monotherapy arms and every 3 weeks for participants randomized to the MK-4280A, MK-7684A, or MK-4830+pembrolizumab arms. Refer to Section 6.1.1.2 for Second Course treatment information for participants in closed arms.
Progression and Subsequent Antineoplastic Therapy Status			X	X	X	X	All progression events and anticancer therapy will be recorded during follow-up until time of death or termination of survival follow-up. If a clinical visit is not feasible, follow-up information may be obtained by other means such as telephone or email. Not required for participants in closed arms.

MK-1308A-008-05 FINAL PROTOCOL
08VH4V

Study Period:	Intervention			EOT	Posttreatment			Notes
Visit Number/Title:	Cycle 1	Cycles 2 to 17 (2 to 9 for Q6W schedule)			Safety FU	Efficacy FU	Survival FU	
Cycle Day	1	1		DC	30 days after last dose			
Scheduling Window (days):	±3	±3			+7	Q9W ±7	Q12W ±14	
12-lead ECG	X	X*	X					*As clinically indicated.
ECOG Performance Status	X	X	X		X			Must be performed before treatment at each cycle.
AE/SAE review								AEs monitored up to 30 days after last dose. SAEs monitored up to 90 days and pregnancy monitored up to 120 days after last dose, or 30 days after last dose if participant starts a new anticancer therapy, whichever is sooner. Participants on the 6 weeks dosing schedule will require a safety phone call at C1D22. The site is to record the call and any findings in the source documents. Further procedures / tests are to be scheduled by the site as clinically indicated and entered in an “unscheduled visit” module in the CRF. Refer to Section 8.3 for safety monitoring information for participants in closed arms.
Laboratory Assessments								

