2.3 Benefit/Risk Assessment

Pembrolizumab monotherapy has shown significant activity in the setting of dMMR/MSI-H mCRC in both first line and later settings. However, the benefit is not universal; in the KEYNOTE-177 study approximately 40% of participants showed disease progression soon after beginning treatment.

The addition of a CTLA-4 antibody (ie, ipilimumab), in an uncontrolled dMMR/MSI-H cohort, has appeared to increase the effectiveness of immunotherapeutic approaches against these tumors. Participants with dMMR/MSI-H CRC treated with both CTLA-4 and PD-1 inhibition had a response rate of 62% and 12-month PFS of 76% [Lenz, H. J., et al 2020] whereas pembrolizumab monotherapy had a response rate of 44% and 12-month PFS of 55% [Andre, T., et al 2020]. However, these approaches have never been directly compared, which is the goal of this study.

The existing preclinical and early clinical data suggest that inhibiting other immune checkpoint molecules in combination with PD-1 blockade is a promising therapeutic strategy and that the risk/benefit assessment for participants in this study will be favorable.

Phase 1 studies have shown that MK-4830 and MK-7684 as monotherapy or in combination with pembrolizumab can potentially enhance antitumor efficacy in patients with solid tumors (refer to respective IBs and Section 2.1). Also, preliminary results support the use of MK-1308 and MK-4280 in combination with pembrolizumab (refer to respective IBs and Section 2.1). An advantage of the platform study design is that it will allow rapid, concurrent evaluation of multiple investigational agents in chemotherapy refractory and previously untreated participants with metastatic dMMR/MSI-H CRC. This may identify new combination interventions with improved responses over those historically achieved with current treatment options. Therefore, a potential benefit may be faster clinical development of novel interventions benefiting this particular patient population, while reducing exposure of participants to interventions that do not show improved clinical benefit. Nevertheless, combination therapy might prove to have greater toxicity rates, particularly with respect to colitis and hepatitis. A goal of this study will be to formally assess AE and SAE rates.

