6.6 Dose Modification (Escalation/Titration/Other)

6.6.1 Immune-Related Events and Dose Modification (Withhold, Treat, Discontinue)

Dose Modification and Toxicity Management for Immune-related AEs Associated With Pembrolizumab Monotherapy, Coformulations, or IO Combinations

AEs associated with pembrolizumab monotherapy, coformulation, or IO combination exposure may represent an immune-related response. These irAEs may occur shortly after the first dose or several months after the last dose of pembrolizumab monotherapy, coformulation, or IO combination treatment and may affect more than one body system simultaneously. Therefore, early recognition and initiation of treatment is critical to reduce complications. Based on existing clinical study data, most irAEs were reversible and could be managed with interruptions of pembrolizumab monotherapy, coformulation, or IO combination administration of corticosteroids and/or other supportive care. For suspected irAEs, ensure adequate evaluation to confirm etiology or exclude other causes. Additional procedures or tests such as bronchoscopy, endoscopy, skin biopsy may be included as part of the evaluation.

Attribution of Toxicity:

When study interventions are administered in combination, attribution of an adverse event to a single component is likely to be difficult. Therefore, while the investigator may attribute a toxicity event to pembrolizumab monotherapy, coformulations, or IO combinations, pembrolizumab monotherapy, coformulations, or IO combinations must be held according to the criteria in the Dose Modification and Toxicity Management Guidelines for Immune-Related Adverse Events.

In these cases where the toxicity is attributed to pembrolizumab coformulations, or IO combinations, reinitiation of pembrolizumab as a monotherapy may be considered after communication with and agreement by the Sponsor.

Holding Study Interventions:

When study interventions are administered in combination and if the AE is considered immune-related, pembrolizumab monotherapy, coformulations, or IO combinations should be held according to recommended Dose Modification criteria.

If the toxicity does not resolve or the criteria for resuming treatment are not met, the participant must be discontinued from pembrolizumab monotherapy, coformulations, or IO combinations.

Restarting Study Interventions:

Participants may restart pembrolizumab monotherapy, coformulations, or IO combinations as described below:

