irAEs	Toxicity Grade (CTCAE v5.0)	Action With Pembrolizumab Monotherapy, Coformulations, or IO Combinations	Corticosteroid and/or Other Therapies	Monitoring and Follow-up
				
 Participants with \geqGrade 2 diarrhea suspecting colitis should consider GI consultation and performing endoscopy to rule out colitis Participants with diarrhea/colitis should be advised to drink liberal quantities of clear fluids. If sufficient oral fluid intake is not feasible, fluid and electrolytes should be substituted via IV infusion
AST or ALT Elevation or Increased Bilirubin	Grade 2 ^a	Withhold	
 Administer corticosteroids (initial dose of 0.5 to 1 mg/kg prednisone or equivalent) followed by taper 	
 Monitor with liver function tests (consider weekly or more frequently until liver enzyme value returned to baseline or is stable)
	Grade 3 ^b or 4 ^c	Permanently discontinue	
 Administer corticosteroids (initial dose of 1 to 2 mg/kg prednisone or equivalent) followed by taper 	
T1DM or Hyperglycemia	New onset T1DM or Grade 3 or 4 hyperglycemia associated with evidence of β -cell failure	Withhold ^d	
 Initiate insulin replacement therapy for participants with T1DM Administer antihyperglycemic in participants with hyperglycemia 	
 Monitor participants for hyperglycemia or other signs and symptoms of diabetes
Hypophysitis	Grade 2	Withhold	
 Administer corticosteroids and initiate hormonal replacements as clinically indicated 	
 Monitor for signs and symptoms of hypophysitis (including hypopituitarism and adrenal insufficiency)
	Grade 3 or 4	Withhold or permanently discontinue ^d		

irAEs	Toxicity Grade (CTCAE v5.0)	Action With Pembrolizumab Monotherapy, Coformulations, or IO Combinations	Corticosteroid and/or Other Therapies	Monitoring and Follow-up
Hyperthyroidism	Grade 2	Continue	
 Treat with nonselective beta-blockers (eg, propranolol) or thionamides as appropriate 	
 Monitor for signs and symptoms of thyroid disorders
	Grade 3 or 4	Withhold or permanently discontinue ^d		

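### Minor safety improvement: Cohort A draws blood at C1D22 but schedules no hematology/chemistry there, so the first post-dose panel comes at day 42 instead of day 21

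*Combined protocol and SAP*

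**What the plan says.** **Cohort A.** The Table 1 row is "Hematology/Chemistry X X* X X X X Collect predose". Its six marks fall at Screening, C1D1, C2D1, Day 1 of Cycles 3-17, EOT and Safety Follow-up. C1D22 and C2D22 are blank. The C1D1 sample is taken before dosing.

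**The C1D22 visit.** Vital signs and a directed examination are marked, with no remote option (that is offered at C2D22). Blood is drawn under the row "Thyroid Function Tests (TSH, T3, T4), Cortisol, and ACTH X X* X X X X X", whose third mark is C1D22.

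**Cohort B.** Table 2 has "Hematology/Chemistry X X* X X X X X Collect Predose", with marks at Day 22 of Cycle 1 and of later cycles. That column applies to the Q6W regimens, which are MK-1308A and pembrolizumab monotherapy, the two Cohort A arms.

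**Second Course.** Table 3 handles the same time point differently: "Participants on the 6 weeks dosing schedule will require a safety phone call at C1D22", with further tests only if clinically indicated.

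**Risk text.** Section 6.6.1 says of immune-related events, "These irAEs may occur shortly after the first dose", and that "early recognition and initiation of treatment is critical to reduce complications". Section 2.3 warns that "combination therapy might prove to have greater toxicity rates, particularly with respect to colitis and hepatitis".

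**The concern.** Cohort A participants are having their first exposure to a checkpoint inhibitor, half of them to a CTLA-4/PD-1 doublet. They attend and give blood three weeks in, yet the tests that would show liver, kidney or glucose toxicity are not run. The panel in Appendix 2, Table 15 contains AST, ALT, bilirubin, creatinine and glucose, on which the hepatic, renal and diabetic rows of Table 6 depend.

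Unscheduled tests are allowed, but a rise without symptoms gives nobody a reason to order one. At stake are up to three weeks of delay in work-up and steroids, and the chance that a Grade 3-4 event comes and goes unseen and is followed by a second dose that Table 6 would have ruled out.

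**Working it through.** **Timing.** Days after dose = cycle day − 1, and a Q6W cycle is 6 × 7 = 42 days. C1D22 is day 22 − 1 = 21 (±3: 18-24). C2D1 is day 42 (±3: 39-45). The gap is 42 − 21 = 21 days. Nothing elsewhere in the protocol adds a C1D22 panel for Cohort A. A participant who stops before C2D1 would have one at EOT.

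**Delay and detection.** The documents give neither onset times nor durations, so these are assumptions: onset uniform over days 0 to T, abnormality lasting D days, no unscheduled test.

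Mean wait from onset to the next scheduled panel:
- T = 21: 42 − 10.5 = 31.5 days now; 21 − 10.5 = 10.5 days with the added panel.
- T = 42: 42 − 21 = 21 days now; 21/2 = 10.5 days with it.

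Share still abnormal at a scheduled panel up to and including C2D1 (now → with the added panel):

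| D (days) | Onset days 0-21 | Onset days 0-42 |
|---|---|---|
| 14 | 0% → 67% | 33% → 67% |
| 21 | 0% → 100% | 50% → 100% |
| 28 | 33% → 100% | 67% → 100% |
| 35 | 67% → 100% | 83% → 100% |
| 42 or more | 100% → 100% | 100% → 100% |

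For T = 21 the current share is P(t + D ≥ 42); at D = 28 this is P(t ≥ 14) = 7/21 = 33%. For T = 42 it is D/42 now and min(1, 2D/42) with the panel. Simulating both visits uniformly within their ±3-day windows shifts the shares by up to about 6 percentage points (T = 21, D = 21: 4% → 94%) and gives mean waits of 31.5 and 11.3 days for T = 21.

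**Yield.** If 1% to 5% of participants (assumed) have such an onset in days 0-21, that is 1 to 5 per 100, or 1/0.01 = 100 down to 1/0.05 = 20 extra panels per case. For scale, Section 2.1 reports Grade 3-4 events of every kind, at any time, in 13-16% on pembrolizumab in previously treated MSI-H disease. It names increased ALT among the commonest, without a rate or timing.

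**Effect on treatment under Table 6.**
- Grade 2 hepatic irAE: withhold and give corticosteroids. Liver tests follow, with the advice to "consider weekly or more frequently until liver enzyme value returned to baseline or is stable". The taper starts at Grade 1 or below and lasts at least 4 weeks, and dosing resumes after it. If the taper could begin on the day of detection, resumption is no earlier than 21 + 28 = day 49. Even detection on day 18 gives day 46, past the C2D1 window, which closes on day 45. Dose 2 is late.
- Grade 3-4 hepatic or renal irAE: permanent discontinuation.
- Treatment also stops permanently if the event has not resolved, or steroids are not down to 10 mg/day, within 12 weeks (84 days) of the last dose. Detection at day 42 leaves 84 − 42 = 42 days, or 14 after allowing a 28-day taper. Detection at day 21 leaves 63, or 35. The limit is 10 mg/day, not zero, so the real room is somewhat larger in both cases. For a longer-lasting event, finding it sooner may keep a participant on therapy.

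**The case against.** The current schedule is coherent. Every dose is preceded by a panel and no dose is due at Day 22. Symptoms, examination and vital signs are checked at C1D22, and extra tests may be ordered at any time (Appendix 2). Unscheduled results that change management are recorded (Section 8.3.5), and unscheduled tests also count towards the Hy's Law criteria (Section 8.4.7). Abnormalities lasting 42 days or more are found before dose 2 in either case. Section 2.3 also reports no new safety signals for these combinations relative to monotherapy, and Section 4.3.1 says the 25 mg quavonlimab dose was safer than the higher doses. All of this stands and limits the size of the gain. It does not help the participant whose enzymes rise silently.

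Two stronger readings are tempting. A reader might infer from Tables 1 and 2 that the blank cell is a mistake. The documents do not show that. Section 8.11.2 gives Cohort B a Day 22 visit in every Q6W cycle, which may exist to match that cohort's Q3W arms, and Cohort A has none. Table 3 shows that a lighter C1D22 check can be deliberate, though it concerns people who have already been through a first course.

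A reader might also infer that the extra panel is free, because no dose falls at Day 22 and the C2D1 panel is predose. Table 6 says otherwise. A Grade 2 hepatic irAE found at day 21 delays dose 2, and a Grade 3-4 event ends treatment even if it would have settled before C2D1. Discontinuation due to AEs is a secondary endpoint (Section 3) and is summarised in Section 9.6.2, so the recorded rates can move.

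Finally, the point may be moot. Section 1.1 gives about 60 months in total and about 3 years per participant, implying roughly 60 − 36 = 24 months of enrollment. Amendment 05 cites a letter of 16-DEC-2024, over 45 months after the original protocol of 22-FEB-2021. Completed enrollment is plausible, but no document states it.

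**Conclusion.** The point holds as a minor patient-safety improvement. The first scheduled post-dose panel in Cohort A is at day 42 and could be at day 21, using a visit and a blood draw that already exist. The sponsor already accepts this test at this visit for the same regimens in Cohort B.

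The gain is earlier detection, by up to about 21 days, of asymptomatic hepatic, renal or glucose irAEs that begin in the first three weeks. It includes Grade 3-4 hepatic or renal events that resolve before C2D1 and would now be followed by redosing. The timing follows from the schedule alone. The waits, detection shares and yield rest on assumed onset, duration and incidence, and they measure detection, not benefit. No document shows harm from the present interval.

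AE and discontinuation rates in Cohort A may rise somewhat. Both arms share the schedule, so how often participants are tested would not differ by arm.

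**What to change.** First establish whether any Cohort A participants have yet to pass C1D22. If none remain, no change is needed. If some do, mark hematology/chemistry at C1D22 in Table 1.

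The cost is one local panel per participant at an existing draw (scheduled on-treatment panels go from 1 + 1 + 15 = 17 to 18), plus repeat tests under Section 8.3.5 for clinically significant values. Some transient abnormalities will be found that would have resolved unseen. Those judged immune-related bring the Table 6 actions: steroids, a late second dose or discontinuation. No new visit and no change of analysis method is needed. If the mark is added part-way through enrollment, the report should say from when, because AE and discontinuation rates before and after are not quite comparable.

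The change does not address pancreatitis, since Appendix 2 takes amylase and lipase only at screening, EOT and the 30-day follow-up.
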